Upon consent and enrollment in the study, relevant subject information will be relayed to the Barnes Jewish Hospital (BJH) Investigational Pharmacy. Prior to proceeding to the operating room for lower extremity amputation, the patients will be randomized 1:1 by the BJH Investigational Pharmacy to either placebo saline infusion (twice daily) or a standard adult intravenous dose of NAC (1200mg twice daily) for 6 days post-amputation during the usual post-operative inpatient extremity off-loading and stump monitoring period. The pharmacy will maintain blinding, with no member of the investigational team having access to the record until the conclusion of the trial.

Early Withdrawal of Subjects

Patients unable to tolerate the administration of the drug will be withdrawn from the study at any point during their hospitalization and will continue to be monitored until their condition stabilizes. Patients unable to participate in the Post-operative Day 0 Non-invasive Laser Assisted Fluorescence Angiography (LAFA) will be withdrawn from the study at that time point and will not receive the investigational product. Subjects for which continuous IV access is not medically indicated during the 6 day study drug administration period may be withdrawn from the study. Patients unable to participate in follow-up appointments will also be withdrawn from the study.

When and How to Withdraw Subjects

Patients unable to tolerate the administration of the drug will be withdrawn from the study trial at any point during their hospitalization. Patients unable to participate in follow-up appointments will also be withdrawn from the study. They will continue to be monitored for adverse events as inpatients for the duration of their hospitalization. Patients unable to participate in the Post-operative Day 0 Non-invasive Laser Assisted Fluorescence Angiography (LAFA) will be withdrawn from the study at that time point and will not receive the investigational product. No further study follow up will be required.

Data Collection and Follow-up for Withdrawn Subjects

Patient data will be collected up until time of withdrawal from the study and pooled into the collective analysis along with all other patients.

Study Drug

Description

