Medications will be prepared by the research pharmacy and delivered to the treating nurse; study drug will be blinded to the research team and the study participant. The research pharmacy will

maintain documentation of medication procurement and preparation, as well as randomization, dispensing, and accountability logs. All medications will be stored in a secure location within the research pharmacy and maintained under controlled environmental conditions. Unused doses will be returned to the research pharmacy, whereas used or unwanted partially infused doses will be destroyed on the nursing unit per policy.

Study Procedures

Screening for Eligibility

As discussed in 2.c, subjects that meet study inclusion and exclusion criteria, who are undergoing an elective above-knee or below-knee amputation at the Washington University School of Medicine-affiliated BJH, will be included in this pilot clinical trial.

Potential subjects will be screened by reviewing the weekly operative schedule, and via referral from vascular surgery faculty study co-investigators. Prior to the scheduled operation, eligible patients will be approached for informed consent. Informed consent will be obtained by a member of the vascular surgery research team in accordance with institutional regulations, prior to any further actions in the study. After informed consent is obtained, a baseline clinical evaluation will be performed including lower extremity anthropometric evaluation, medical history and vital signs documentation. Per standard clinical procedures, all patients will also be evaluated by preoperative anesthesia services. Subjects may **participate in the study a second time on ipsilateral or contralateral site if all Inclusion /Exclusion is reviewed and verified prior to second surgery. Patient records from an outside hospital or facility may be obtained and used for screening and/or follow up in patient care.**

Schedule of Measurements

A. Non-invasive Laser Assisted Fluorescence Angiography (LAFA)

Location of Procedure:

- Barnes-Jewish Hospital Operating Rooms
- 4400/8300/7400/7500 Inpatient Hospital Units
- Other Hospital Units also housing vascular surgery patients

Time of Data Collection:

- **Postoperative Day 0:** Obtained in the operating room after amputation, but before placement of dressings.
- **Postoperative Day3:** Obtained following dressing removal at bedside in the inpatient hospital unit.

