- **Day 0 (Day of Operation):** If possible and/or equipment available, obtained prior to the operation at the anticipated level of the amputation.
- **Postoperative Day3:** If possible and/or equipment available, obtained following dressing removal at bedside in the inpatient hospital unit.
- **Postoperative Day5:** If possible and/or equipment available, also obtained at bedside in the inpatient hospital unit if the patient is still in-house.

[figure not shown]
Contraindications to Measurement:

- Patient refusal/inability to participate in measurement before or during data collection
- Patient SpO₂ < 92%, Patient is febrile >38°C, unstable vitals
- Patient unable to lie supine for at least 20 minutes during measurement collection
- Patient unable to breathe normobaric oxygen
- *A contraindication to TcPO₂ measurements does not exclude the patient from other measurements within the study protocol

Protocol Steps:

1. Ensure patient meets the eligibility criteria above.
2. Keep patient covered, and expose the anticipated amputation site or at the amputation stump. Do not elevate the site throughout the measurement collection.
3. Select 4 collection sites as follows:
 1. 3 sites on the anticipated amputation site the stump site, one per section. (Figure 1)
 2. 1 control site on the left anterior chest in indicated on figure. (Figure 1)
4. Electrodes will be placed as per TCM Manual instructions, replicated below with the following specifications:
 1. Temp. set to 45°C.
 2. Do not place probes on scar tissue or dermatologically compromised sites.
 3. Do not place probe over bone.
5. After 15-20 minutes, record the TcPO₂ numbers in all 4 sites. Mark the location of the sites for future measurements to ensure a consistent location for measurement and control (days 2 and 4).
6. Remove probes from patients.

Figure 1

listed

or at

area

Data Analysis:

After TcPO₂ measurements have been collected, the 3 amputation site measurements will be averaged to calculate a mean TcPO₂. The control site measurement on the operated leg will be used to calculate a Regional perfusion index (Mean TcPO₂ / Chest/Control TcPO₂). The non-operated leg measurement site (compared against the operated site) will be used to determine if lower TcPO₂ values in the amputation site are due to regional or systemic oxygenation.

How to place an electrode

Step	Action
------	--------

1. Calibrate the tcpO₂ electrode.

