 23. Kapp, M.B., *Ethical and legal issues in research involving human subjects: do you want a piece of me?* J Clin Pathol, 2006. **59**(4): p. 335-9.
 24. Holdiness, M.R., *Clinical pharmacokinetics of N-acetylcysteine.* Clin Pharmacokinet, 1991. **20**(2): p. 123-34.

STATISTICAL ANALYSIS PLAN

**Protocol Title: N-Acetyl-Cysteine for Healing of
Amputation Stumps in the Setting of Diabetes**

NCT03253328

**Protocol Version 11.0
Date: March 26, 2020**

Statistical Plan

Sample Size Determination and Power

The purpose of this study is to obtain sufficient preliminary data to determine the sample size necessary for a future large definitive clinical trial. For this pilot study, we plan to enroll 25 patients in each group, allowing for a dropout rate of 10% per group.

We emphasize that effect size (the expected difference in primary outcome between the treatment and control groups) should not be determined by the pilot study. Rather it is determined by the minimum clinically important difference. However, the effect size from the pilot give us some ideas about possible achievable difference.

Interim Monitoring and Early Stopping

An interim analysis will be conducted once >30 patients are enrolled in the study. Analysis will focus on determining differences between NAC and control group. Interim analysis will help determine early differences between the study groups and safety profile of study intervention. The investigators may end the study early depending on study findings, safety profile of the data, and/or if data is adequate for a peer-reviewed publication.

Analysis Plan

Data analysis include (1) the partition of variation of outcome measurements into within and between patient components to obtain standard deviation of measurements, intra-class correlation of the measurements, (2) use of appropriate regression model (GEE or mixed effect regression) to compare the outcome measurements between two groups, while accounting for the intra-class correlation. Interpretation of analysis should be made within the context of a pilot study where we have a pre-specified hypothesis but do not have power analysis for testing the hypothesis.

Statistical Methods

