One of the main study outcomes (and in the future large study) is the stump perfusion assessment, which is a continuous variable measured three times (D0, D3, and D5) after treatment. Based on this longitudinal repeated measurement study design, the preliminary data needed for designing future study include: (1) variance of single measurement, (2) covariance (correlation) among the repeated measurements over time within an individual, (3) level of outcome measurements in patients with and without the treatment.

Missing Outcome Data

Not applicable

Unblinding Procedures

The BJH Investigational Pharmacy will maintain a record of each patient's medical record number and to which arm of the study they were assigned. No member of the vascular surgery investigational team will have access to this information. This will serve to maintain blinding and reduce any unwanted during the trial and subsequent analysis of collected data. Un-blinding of patient data will occur during the interim analysis, and at the end of the study. For un-blinding the pharmacy will then un-blind the study to the investigators such that appropriate conclusions can be made regarding the efficacy of the investigational agent.

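### The SD and single intra-class correlation meant to size the next trial come from a partition that names no visit or arm term, over three readings that are not replicates

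*Combined protocol and SAP*

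**What the plan says.** The SAP (Sample Size Determination and Power) states the aim: "The purpose of this study is to obtain sufficient preliminary data to determine the sample size necessary for a future large definitive clinical trial". The same section takes the effect size of that later trial from the minimum clinically important difference, not from the pilot. The inputs the pilot does supply are therefore mainly variability and correlation.

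The Analysis Plan (identical in protocol and SAP) has two steps. Step 1 is "the partition of variation of outcome measurements into within and between patient components", which is to yield the SD and the intra-class correlation. Step 2 is a GEE or mixed model comparing the groups while allowing for that correlation. No visit term, arm term, baseline term or covariance structure is named for either step.

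Statistical Methods lists what the next trial needs. The list includes the variance of a single measurement and the "covariance (correlation) among the repeated measurements over time within an individual". It describes D0, D3 and D5 as all falling after treatment.

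The Schedule of Measurements gives the conditions on D0. LAFA: "Obtained in the operating room after amputation, but before placement of dressings". TcPO2: "obtained prior to the operation at the anticipated level of the amputation". D3 and D5 are bedside readings of the stump. Under Treatment Regimen, the first infusion is given once the patient has left the operating room, so both D0 readings precede treatment.

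**The concern.** An ICC from a within/between partition treats a patient's readings as interchangeable. Here they differ in time, place and relation to treatment and, for D0 TcPO2, in tissue, since no stump exists yet. Two separate problems follow.

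- **No named visit or arm term.** A literal two-component partition puts any average change from D0 to D5 into the within-patient component, which makes the SD too high and the ICC too low. With no arm term, a treatment difference is also absorbed into the variance components.
- **One SD and one ICC.** Even with visit fitted, a single pair of values assumes the same variance on all three days and the same correlation for D0-D3, D0-D5 and D3-D5. It cannot supply the covariance over time that Statistical Methods asks for.

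At stake is the usefulness of the pilot's main product. If these values go into a sample size formula, the next trial may be too large or too small, depending on its design and on what the data look like.

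**Working it through.** **The plan's own figure.** The only size stated is "we plan to enroll 25 patients in each group, allowing for a dropout rate of 10% per group". This is consistent with 22 evaluable per group (22/0.9 = 24.4, rounded up to 25), or about 50 × 0.9 = 45 patients in all. It cannot be derived, because the plan says that the investigators "do not have power analysis for testing the hypothesis" and gives no SD, alpha or power. No SD, ICC or next-trial size is stated, so there is nothing further to reproduce.

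**Assumed inputs (none is in the documents).** Within-day variance 1; true correlation ρ = 0.60; day means rising evenly by 0.5 SD or 1 SD from D0 to D5; k = 3 days.

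**Step 1: literal one-way partition, 1 SD rise (means 0, 0.5, 1.0).**
- MSB = kρ + (1 − ρ) = 3(0.60) + 0.40 = 2.20
- Variance of the day means = (0.25 + 0 + 0.25)/2 = 0.25
- MSW = 0.40 + 0.25 = 0.65
- Between-patient variance = (2.20 − 0.65)/3 = 0.517
- Total = 0.517 + 0.65 = 1.167, so SD = 1.08 and ICC = 0.517/1.167 = 0.443

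For a 0.5 SD rise (means 0, 0.25, 0.5): MSW = 0.40 + 0.0625 = 0.4625, between = 0.579, total = 1.042, SD = 1.02, ICC = 0.556.

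Simulated random-intercept fits (50 patients, 150 runs, 1 SD rise) agree. Without visit, SD is 1.07 and ICC 0.44; with visit, 0.99 and 0.60.

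**Step 2: effect on the next trial.** Size is proportional to the variance of the analysed quantity. The ratio is that variance with the partition's SD and ICC (as r), over its value with SD 1 and r = 0.60. N per arm assumes a difference of 0.5 within-day SD, two-sided 5% and 80% power; rounding up makes the N ratios differ slightly.

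| Design | Variance | Ratio, 0.5 SD rise | Ratio, 1 SD rise | N per arm, correct → partition (1 SD rise) |
|---|---|---|---|---|
| Mean of three visits | SD²(1 + 2r)/3 | 1.00 | 1.00 | 47 → 47 |
| Single visit | SD² | 1.04 | 1.17 | 63 → 74 |
| Baseline-adjusted | SD²(1 − r²) | 1.12 | 1.47 | 41 → 59 |
| Change from D0 | 2·SD²(1 − r) | 1.16 | 1.62 | 51 → 82 |

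For example, baseline-adjusted at 1 SD is 1.167 × (1 − 0.443²)/(1 − 0.36) = 1.47, and change score is 0.65/0.40 = 1.625, shown as 1.62. Other true correlations at a 1 SD rise give a change-score N of 76 → 107 (ρ = 0.4) and 26 → 57 (ρ = 0.8). If means do not shift and variances and correlations are equal, every ratio is 1.00.

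**Step 3: visit fitted, but one pooled SD and ICC.**
- Unequal correlations, assumed 0.5 (D0-D3), 0.4 (D0-D5) and 0.7 (D3-D5): the average is 0.533. A baseline-adjusted D5 design is then sized at (1 − 0.533²)/(1 − 0.4²) = 0.716/0.84 = 0.85 of its need.
- Unequal SDs, assumed 0.6 on D0 and 1.0 on D3 and D5: the pooled variance is (0.36 + 1 + 1)/3 = 0.787, so the pooled SD is 0.89 where D5 has 1.0. The simulation also gives 0.89.

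**Step 4: both effects together.** With correlations 0.5/0.4/0.7, no visit term and a 1 SD rise: MSB = 2.067, MSW = 0.717, between = 0.45, total = 1.167, ICC = 0.386. The baseline-adjusted ratio is 1.167 × (1 − 0.386²)/0.84 = 1.18. For a 0.5 SD rise, the same steps give 0.94.

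**The case against.** The strongest reply is that silence is not exclusion. A mixed model with fixed visit effects also partitions variance into within- and between-patient parts, and nothing says that step 1 must be a bare one-way split. Statistical Methods also shows the right intent: it wants the variance of a single measurement, covariance over time, and levels with and without treatment. This stands. A reader might infer that the SAP leaves visit out; the documents show only that it does not name it.

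A reader might also infer that the next trial will be mis-sized, or that it must rest on the D5 SD and the D0-D5 correlation. Neither is supported. Primary Aim 1 refers to perfusion by postoperative day 5, but Statistical Methods describes the future outcome as a three-occasion longitudinal measure, and no document fixes a change-score or baseline-adjusted analysis. For a balanced three-visit mean, the mean shift does no harm at all. Errors in opposite directions can also partly cancel, as Step 4 shows.

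Two further points hold in part. With about 45 patients, a normal-theory 95% interval for a variance runs from roughly 0.69 to 1.60 times the estimate, so the milder 12% to 16% inflation is smaller than sampling noise, although it is systematic. And D0 LAFA images the same stump with the same device as D3 and D5, so the unlike conditions are sharper for TcPO2.

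What the reply does not answer is that the Analysis Plan is the only place that says how these quantities are obtained, and it promises one SD and one ICC. A single correlation cannot stand in for three, whether or not visit is fitted.

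**Conclusion.** The point holds as a gap between the method in the Analysis Plan and the inputs listed in Statistical Methods. The partition names no visit or arm term, and its single SD and ICC assume an exchangeability that the measurement schedule contradicts. D0 is also described as post-treatment when both D0 readings come before the first infusion.

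The consequence is conditional. Under ρ = 0.60 and the literal reading, the size ratio runs from 1.00 to 1.16 for a 0.5 SD rise and from 1.00 to 1.62 for a 1 SD rise, depending on the design. Unequal correlations alone can push it the other way, to 0.85 for a baseline-adjusted design. Every shift, correlation and SD behind these figures is an assumption, so they show sensitivity and do not predict an error. The correction is still worth making, because it bears on what the pilot was set up to deliver and needs no new data.

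**What to change.** In the SAP's Analysis Plan and Statistical Methods, and in the matching protocol text:

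1. Label D0 as the pre-treatment baseline, and D3 and D5 as post-treatment.
2. Replace step 1 with one mixed model per outcome, LAFA and TcPO2 separately, with arm-by-day means and an unstructured 3 × 3 covariance.
3. Report the SD on each day and the D0-D3, D0-D5 and D3-D5 correlations, with confidence intervals, in place of a single pooled SD and ICC.
4. Name a fallback in case the model does not converge: a simpler correlation structure that keeps day-specific variances.

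The cost is a wording change and no new data. The downside is precision. Six covariance parameters must be estimated from possibly fewer than 45 patients with complete data, since D5 readings are lost on discharge, TcPO2 is taken only where feasible, and the study may stop after an interim analysis at just over 30 enrolled. The confidence intervals will show that uncertainty to whoever sizes the next trial.

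### The SAP permits GEE with 22–25 patients per arm (about 13–15 at the interim) and names no small-sample correction; uncorrected, its intervals would be modestly too narrow.

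*Combined protocol and SAP*

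**What the plan says.** The Analysis Plan in the SAP, repeated in the protocol's Statistical Plan, provides for "use of appropriate regression model (GEE or mixed effect regression) to compare the outcome measurements between two groups", accounting for within-patient correlation. It does not choose between the two methods. It gives no working correlation, type of standard error, reference distribution, degrees of freedom or small-sample correction.

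On numbers, the sample size section states "we plan to enroll 25 patients in each group, allowing for a dropout rate of 10% per group". On the interim, the SAP says "An interim analysis will be conducted once >30 patients are enrolled in the study" and "Analysis will focus on determining differences between NAC and control group". It allows the investigators to stop early on what they find. Under Statistical Methods, stump perfusion "is a continuous variable measured three times (D0, D3, and D5) after treatment".

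Neither document gives a significance level or confidence level. The Analysis Plan adds "Interpretation of analysis should be made within the context of a pilot study where we have a pre-specified hypothesis", and that the investigators "do not have power analysis for testing the hypothesis".

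**The concern.** The usual GEE sandwich variance is justified when there are many independent clusters. Here the clusters are patients, and there are few. With few clusters the uncorrected sandwich is biased downwards. Comparing the resulting ratio with a normal rather than a t distribution adds a second error in the same direction. The interval for the NAC–placebo difference is then too narrow, and a test based on it rejects too often.

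The effect is larger at the interim, which has fewer patients and can lead to early termination. It grows again if POD 5 perfusion is missing. The protocol's LAFA schedule omits the POD 5 measurement once a patient has been discharged, and the infusion table anticipates discharge on that day. Interval width matters even if no hypothesis is tested, because the trial is meant to inform the design of a larger one.

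**Working it through.** **Inputs from the documents**
- 25 per arm with 10% dropout: 25 × 0.9 = 22.5, so about 22 per arm. No power, effect size, SD or alpha is given, so the figure of 25 cannot be derived from a sample-size formula. Only the dropout arithmetic can be checked, and it is consistent: 22 / 0.9 = 24.4, rounded up to 25.
- Allocation is 1:1 (Randomization Method and Blinding).
- The interim comes after more than 30 are enrolled: 31 × 0.9 = 27.9, so 27–28 patients, or about 13.5 per arm.
- The protocol pools withdrawn patients' data into the analysis, so the clusters could be as many as 25 per arm at the end and 15.5 at the interim (31 / 2).
- Three perfusion measurements per patient.

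**Assumptions**
- Two-sided 5% level (95% intervals).
- 10% dropout also applies at the interim.
- Normal outcomes and, in the simulation, exchangeable correlation.

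**Closed form, complete balanced data**

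With n per arm, the treatment contrast is a difference in arm means. The uncorrected sandwich divides each arm's sum of squares by n instead of n − 1, so its standard error is √((n − 1)/n) times the unbiased one. The actual error with a normal reference is therefore

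2 × P(t with 2n − 2 df > 1.96 × √((n − 1)/n)).

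For n = 22, √(21/22) = 0.977, so the standard error is 2.3% too small. The effective cut-off is 1.96 × 0.977 = 1.915 on 42 df, and the error is 6.2%. For n = 13.5, √(12.5/13.5) = 0.962 (3.8% too small), the cut-off is 1.886 on 25 df, and the error is 7.1%.

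The last column below is the width of a correct t interval relative to the uncorrected one, t / (1.96 × √((n − 1)/n)). For example, 2.018 / 1.915 = 1.054 and 2.060 / 1.886 = 1.092.

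| n per arm | Sandwich SE, normal ref. | Sandwich SE, t ref. | Unbiased SE, normal ref. | Unbiased SE, t ref. | Correct interval wider by |
|---|---|---|---|---|---|
| 22 (final) | 6.2% | 5.5% | 5.7% | 5.0% | 5.4% |
| 25 (final, withdrawn kept) | 6.1% | 5.5% | 5.6% | 5.0% | 4.7% |
| 13.5 (interim) | 7.1% | 5.9% | 6.1% | 5.0% | 9.2% |
| 15.5 (interim, withdrawn kept) | 6.8% | 5.8% | 6.0% | 5.0% | 7.9% |

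The third and fourth columns split the excess. At 22 per arm the standard error alone adds 0.5 points and the normal reference alone 0.7 points, so each accounts for roughly half.

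**Simulation under no treatment effect**

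Exchangeable GEE was fitted to three visits, with 4,000 runs per setting (Monte Carlo standard error about 0.4 points). Within-patient correlation was 0.5 throughout, with 0.8 also tried for the POD 5 contrast with missing data. Either an overall treatment effect or the POD 5 contrast was tested. Data were complete, or had 30% missing at POD 5 and 10% at POD 3.

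| Patients | Uncorrected, normal ref. | Mancl-DeRouen, normal ref. | Mancl-DeRouen, t(N − 2) |
|---|---|---|---|
| 44 (22 + 22) | 6.1–7.1% | 4.9–5.5% | 4.3–4.9% |
| 27 (14 + 13) | 6.5–8.5% | 4.8–5.6% | 3.8–4.5% |

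The 8.5% is the POD 5 contrast at the interim with 30% of POD 5 values missing and correlation 0.5. At correlation 0.8 the same setting gave 6.9%. The simulation agrees with the closed form, and the correction brings the error back to about 5%.

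**The case against.** **The inflation is conditional.** A reader might infer that the plan's standard errors are too small and its false-positive rate exceeds 5%. The documents do not say that. It takes three choices that the SAP leaves open: GEE rather than a mixed model, an uncorrected sandwich, and a normal reference. The SAP equally permits a mixed model, and it does not forbid a correction. This stands, and it limits the point to what happens if the usual GEE default is used.

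**No 5% level is stated, and the trial is a pilot.** Both are true. The quantities the SAP lists for designing the next trial (variance, within-patient correlation, group levels) are not altered by a biased standard error of the contrast. But the SAP also plans a between-group comparison and refers to a pre-specified hypothesis. An interval for that comparison is too narrow whether or not anyone tests at 5%.

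**Larger figures are tempting.** Rates of 9–10% can be produced with a baseline-adjusted model, heavy POD 5 missingness, or an analysis of diabetic patients only. The documents specify no such adjustment, give no missingness rate or diabetic share, and plan no between-arm test in diabetics. Those figures are not relied on here.

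**The interim has a bigger problem.** Two looks (27 then 44 patients), each at an assumed 5%, give 8.0% overall even with a correct t test each time, and 10.5% with the uncorrected sandwich and normal reference. A reader might infer that correcting the standard error makes the interim safe. It does not, because the missing boundary is a separate matter.

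**A linear mixed model does not suit every outcome.** This stands. The sentence covers all outcome measurements, and stump healing, the second primary aim, is assessed with a score whose scale is not defined.

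**Conclusion.** The point holds in a limited form. The SAP permits a method that, in its usual uncorrected form, is mildly anti-conservative at these sample sizes, and it names no correction. The excess over an assumed 5% level is about 1 point at the final analysis and about 2 at the interim. At the interim it is up to about 3.5 points if 30% of POD 5 values are missing. Keeping withdrawn patients as clusters lowers the complete-data figures only slightly, to 6.1% and 6.8%. These sizes assume normal outcomes and, for the simulated range, exchangeable correlation.

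This is an inexpensive improvement to the analysis. It is not evidence that the trial's conclusions will be wrong.

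**What to change.** In the Analysis Plan of both the SAP and the protocol:
- For the continuous perfusion outcome, replace the open choice of method with a REML linear mixed model for repeated measures with Kenward-Roger degrees of freedom, at both the interim and final analyses.
- Wherever GEE is used, for example for a non-continuous healing outcome or as a sensitivity analysis, require a bias-corrected sandwich such as Mancl-DeRouen.
- State the confidence level (and alpha, if tests are to be reported).

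The cost is a few lines of text and slightly wider intervals: about 5% wider at the final analysis and 9% at the interim than with uncorrected GEE. Mancl-DeRouen combined with a t reference on N − 2 df was slightly conservative in simulation (3.8–4.9%). The interim boundary needs its own amendment.
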